6.3.3.2 Evaluation of Non-Target Lesions

Complete Response (CR): Disappearance of all non-target lesions and normalization of tumor marker level. All lymph nodes must be non-pathological in size (<10 mm short axis).

Note: If tumor markers are initially above the upper normal limit, they must normalize for a participant to be considered in complete clinical response.

Non-CR/Non-PD: Persistence of one or more non-target lesion(s) and/or maintenance of tumor marker level above the normal limits.

Progressive Disease (PD): Appearance of one or more new lesions and/or *unequivocal progression* of existing non-target lesions. *Unequivocal progression* should not normally trump target lesion status. It must be representative of overall disease status change, not a single lesion increase.

Although a clear progression of "non-target" lesions only is exceptional, the opinion of the treating physician should prevail in such circumstances, and the progression status should be confirmed at a later time by the review panel (or Principal Investigator).

6.3.3.3 Metastatic Bone Lesions

Disease progression is considered if a minimum of two new lesions is observed on bone scan. New lesions seen on first re-staging (at 3 months) may represent disease that was not detected on the baseline scan. In these circumstances, the first re-staging scan then will serve as the baseline comparison for future scans. Participant can be removed at first re-staging at the discretion of the investigator if the clinical scenario is most consistent with disease progression and not "flare" on bone scan. This is consistent with Prostate Cancer Working Group 3 recommendations.(63)

6.3.3.4 Clinical Disease Progression

- The need for chemotherapy or other change in therapy based on increased cancer related symptoms
- Worsening ECOG PS to a PS of 3 or 4 based on cancer (not treatment) related symptoms
- Clinical disease progression can also be determined based on the clinical discretion of the investigator

### 6.3.3.5 Evaluation of Best Overall Response

The best overall response is the best response recorded from the start of the treatment until disease progression/recurrence (taking as reference for progressive disease the smallest measurements recorded since the treatment started). The participant's best response assignment will depend on the achievement of both measurement and confirmation criteria.

Target Lesions	Non-Target Lesions	New Lesions	Overall Response	Best Overall Response when Confirmation is Required*
CR	CR	No	CR	≥4 wks. Confirmation**
CR	Non-CR/Non- PD	No	PR	
CR	Not evaluated	No	PR	>4 wks. Confirmation**
PR	Non-CR/Non- PD/not evaluated	No	PR	
SD	Non-CR/Non- PD/not evaluated	No	SD	Documented at least once > 4 wks. from baseline**
PD	Any	Yes or No	PD	no prior SD, PR or CR

For Participants with Measurable Disease (i.e., Target Disease)

Ar	ıy	PD***	Yes or No	PD			
Ar	ıy	Any	Yes	PD			
* **	See RECIST 1.1 manuscript for further details on what is evidence of a new lesion.						
***	In exceptional circumstances, unequivocal progression in non-target lesions may be accepted as disease progression.						
Note :	Participants with a global deterioration of health status requiring discontinuation of treatment without objective evidence of disease progression at that time should be reported as " symptomatic deterioration ." Every effort should be made to document the objective progression even after discontinuation of treatment.						

# For Participants with Non-Measurable Disease (i.e., Non-Target Disease)

Non-Target Lesions	New Lesions	Overall Response
CR	No	CR
Non-CR/non-PD	No	Non-CR/non-PD*
Not all evaluated	No	not evaluated
Unequivocal PD	Yes or No	PD
Any	Yes	PD

\* 'Non-CR/non-PD' is preferred over 'stable disease' for non-target disease since SD is increasingly used as an endpoint for assessment of efficacy in some trials so to assign this category when no lesions can be measured is not advised

# 6.3.4 Duration of Response

The duration of response is defined by time of sustained >30% decline in PSA from baseline.

# 6.3.5 Overall Survival

Overall Survival is defined as the duration of time from the start of treatment to the time of death..

#### 6.3.6 Response Review

Tumor measurements will be performed in consultation with the Center for Cancer Research Radiology and Imaging Sciences processing service.

#### 6.4 TOXICITY CRITERIA

The following adverse event management guidelines are intended to ensure the safety of each participant while on the study. The descriptions and grading scales found in the revised NCI

Common Terminology Criteria for Adverse Events (CTCAE) version 5.0 will be utilized for AE reporting. All appropriate treatment areas should have access to a copy of the CTCAE version 5.0. A copy of the CTCAE version 5.0 can be downloaded from the CTEP web site (http://ctep.cancer.gov/protocolDevelopment/electronic\_applications/ctc.htm).

# 7 NIH REPORTING REQUIREMENTS/ DATA AND SAFETY MONITORING PLAN

# 7.1 **D**EFINITIONS

Please refer to definitions provided in Policy 801: Reporting Research Events found here.

# 7.2 OHSRP OFFICE OF COMPLIANCE AND TRAINING/IRB REPORTING

7.2.1 Expedited Reporting

Please refer to the reporting requirements in Policy 801: Reporting Research Events and Policy 802 Non-Compliance Human Subjects Research found here. Note: Only IND Safety Reports that meet the definition of an unanticipated problem will need to be reported per these policies.

# 7.2.2 IRB Requirements for PI Reporting at Continuing Review

Please refer to the reporting requirements in Policy 801: Reporting Research Events found here.

# 7.3 NCI CLINICAL DIRECTOR REPORTING

Problems expeditiously reported to the OHSRP in iRIS will also be reported to the NCI Clinical Director. A separate submission is not necessary as reports in iRIS will be available to the Clinical Director.

In addition to those reports, all deaths that occur within 30 days after receiving a research intervention should be reported via email to the Clinical Director unless they are due to progressive disease.

To report these deaths, please send an email describing the circumstances of the death to [name] at [contact] within one business day of learning of the death.

# 7.4 NIH REQUIRED DATA AND SAFETY MONITORING PLAN

7.4.1 Principal Investigator/Research Team

The clinical research team will meet on a weekly regular basis when participants are being actively treated on the trial to discuss each participant. Decisions about dose level enrollment and dose escalation if applicable will be made based on the toxicity data from prior participants.

All data will be collected in a timely manner and reviewed by the principal investigator or a lead associate investigator. Events meeting requirements for expedited reporting as described in section 7.2.1 will be submitted within the appropriate timelines.

The principal investigator will review adverse event and response data on each participant to ensure safety and data accuracy. The principal investigator will personally conduct or supervise the investigation and provide appropriate delegation of responsibilities to other members of the research staff.

# 8 SPONSOR SAFETY REPORTING

# 8.1 **DEFINITIONS**

# 8.1.1 Adverse Event

Any untoward medical occurrence in a patient or clinical investigation subject administered a pharmaceutical product and which does not necessarily have a causal relationship with this treatment. An adverse event (AE) can therefore be any unfavorable and unintended sign (including an abnormal laboratory finding), symptom, or disease temporally associated with the use of a medicinal (investigational) product, whether or not related to the medicinal (investigational) product (ICH E6 (R2)).

# 8.1.2 Serious Adverse Event (SAE)

An adverse event or suspected adverse reaction is considered serious if in the view of the investigator or the sponsor, it results in any of the following:

- Death
- A life-threatening adverse event (see **8.1.3**)
- Inpatient hospitalization or prolongation of existing hospitalization
  - A hospitalization/admission that is pre-planned (i.e., elective or scheduled surgery arranged prior to the start of the study), a planned hospitalization for pre-existing condition, or a procedure required by the protocol, without a serious deterioration in health, is not considered a serious adverse event.
  - A hospitalization/admission that is solely driven by non-medical reasons (e.g., hospitalization for participant convenience) is not considered a serious adverse event.
  - Emergency room visits or stays in observation units that do not result in admission to the hospital would not be considered a serious adverse event. The reason for seeking medical care should be evaluated for meeting one of the other serious criteria.
- Persistent or significant incapacity or substantial disruption of the ability to conduct normal life functions
- A congenital anomaly/birth defect.
- Important medical events that may not result in death, be life-threatening, or require hospitalization may be considered a serious adverse drug experience when, based upon appropriate medical judgment, they may jeopardize the patient or subject and may require medical or surgical intervention to prevent one of the outcomes listed in this definition.

# 8.1.3 Life Threatening

An adverse event or suspected adverse reaction is considered "life-threatening" if, in the view of either the investigator or sponsor, its occurrence places the patient or subject at immediate risk of death. It does not include an adverse event or suspected adverse reaction that, had it occurred in a more severe form, might have caused death. (21CFR312.32)

# 8.1.4 Severity

The severity of each Adverse Event will be assessed utilizing the CTCAE version 5.0.

8.1.5 Relationship to Study Product

All AEs will have their relationship to study product assessed using the terms: related or not related.

- Related There is a reasonable possibility that the study product caused the adverse event. Reasonable possibility means that there is evidence to suggest a causal relationship between the study product and the adverse event.
- Not Related There is not a reasonable possibility that the administration of the study product caused the event.
- 8.2 Assessment of Safety Events

AE information collected will include event description, date of onset, assessment of severity and relationship to study product and alternate etiology (if not related to study product), date of resolution of the event, seriousness and outcome. The assessment of severity and relationship to the study product will be done only by those with the training and authority to make a diagnosis and listed on the Form FDA 1572 as the site principal investigator or sub-investigator. AEs occurring during the collection and reporting period will be documented appropriately regardless of relationship. AEs will be followed through resolution.

For timeframe of recording adverse events, please refer to section **6.1**. All serious adverse events recorded from the time of first investigational product administration must be reported to the sponsor.

SAEs will be:

- Assessed for severity and relationship to study product and alternate etiology (if not related to study product) by a licensed study physician listed on the Form FDA 1572 as the site principal investigator or sub-investigator.
- Recorded on the appropriate SAE report form, the medical record and captured in the clinical database.
- Followed through resolution by a licensed study physician listed on the Form FDA 1572 as the site principal investigator or sub-investigator.

# 8.3 REPORTING OF SERIOUS ADVERSE EVENTS

Any AE that meets protocol-defined serious criteria, or meets the definition of Adverse Event of Special Interest that require expedited reporting must be submitted immediately (within 24 hours of awareness) to OSRO Safety using the CCR SAE report form.

All SAE reporting must include the elements described in 8.2.

SAE reports will be submitted to the Center for Cancer Research (CCR) at: [contact] and to the CCR PI and study coordinator. CCR SAE report form and instructions can be found at:

https://ccrod.cancer.gov/confluence/pages/viewpage.action?pageId=157942842

Following the assessment of the SAE by OSRO, other supporting documentation of the event may be requested by the OSRO Safety and should be provided as soon as possible.

8.4 SAFETY REPORTING CRITERIA TO THE PHARMACEUTICAL COLLABORATORS

All events listed below must be reported in the defined timelines to [contact].

8.4.1 To be sent by OSRO Safety

8.4.1.1 Ellipses Pharma Reporting Requirements - Expedited Reporting

To ensure patient safety, every SAE, regardless of suspected causality, occurring after the patient begins taking study drug and until 30 days after the patient has stopped study treatment will be reported by the Sponsor to Ellipses Pharma via their safety vendor, Simbec-Orion, within 1-2 business days of learning of its occurrence. The MedWatch 3500a form or equivalent will be used to report all SAEs.

Any SAE experienced after this 30 day period should only be reported to Ellipses Pharma if the investigator suspects a causal relationship to the study drug. Recurrent episodes, complications, or progression of the initial SAE must be reported as follow-up to the original episode within 1-2 business days of the sponsor receiving the follow-up information. An SAE occurring at a different time interval or otherwise considered separately as a new event. The investigator must assess and record the relationship of each SAE to each specific study drug (if there is more than one study drug).

Ellipses safety vendor, Simbec-Orion: Email address: [contact] [contact] Back-up SAE [contact]

8.4.1.2 Routine Reporting

The Sponsor will also send the FDA annual report to Ellipses Pharma as agreed upon in the collaborative agreement.

8.4.2 To Be Reported by the Research team

8.4.2.1 Adverse Events of Special Interest (AESI) associated with CRLX101

For all subjects, the following adverse events are categorized as Adverse Events of Special Interest (AESI) associated with CRLX101:

- Infusion-related hypersensitivity reaction(s) of any grade
- Any newly developed cystitis (including Grade 1) in subjects without cystitis at baseline

Any occurrence of hypersensitivity/allergic reactions and/or cystitis a patient experiences associated with CRLX101 must be reported to Ellipses Pharma within 1-2 business days of learning of its occurrence using the OSRO Serious Adverse Event Form.

AESIs will be sent to Ellipses Pharma via their safety vendor, Simbec-Orion by email to: [contact]

Or alternatively by fax to: [contact] or back-up [contact] .

## 8.5 REPORTING PREGNANCY

### 8.5.1 Paternal Exposure

Male patients should refrain from fathering a child or donating sperm during the study and for 120 days following the last dose of study drug.

Pregnancy of the patient's partners is not considered to be an adverse event. However, the outcome of all pregnancies (spontaneous miscarriage, elective termination, ectopic pregnancy, normal birth or congenital abnormality) should if possible be followed up and documented.

The outcome of any conception occurring from the date of the first dose until 120 days after the last dose of study drug should be followed up and documented.

# 8.6 REGULATORY REPORTING FOR STUDIES CONDUCTED UNDER CCR-SPONSORED IND

Following notification from the investigator, CCR, the IND sponsor, will report any suspected adverse reaction that is both serious and unexpected. CCR will report an AE as a suspected adverse reaction only if there is evidence to suggest a causal relationship between the study product and the adverse event. CCR will notify FDA and all participating investigators (i.e., all investigators to whom the sponsor is providing drug under its INDs or under any investigator's IND) in an IND safety report of potential serious risks from clinical trials or any other source, as soon as possible, in accordance to 21 CFR Part 312.32.

All serious events will be reported to the FDA at least annually in a summary format.

# 9 CLINICAL MONITORING

As a sponsor for clinical trials, FDA regulations require the CCR to maintain a monitoring program. The CCR's program allows for confirmation of: study data, specifically data that could affect the interpretation of primary and secondary study endpoints; adherence to the protocol, regulations, ICH E6, and SOPs; and human subjects protection. This is done through independent verification of study data with source documentation focusing on:

- Informed consent process
- Eligibility confirmation
- Drug administration and accountability
- Adverse events monitoring
- Response assessment.

The monitoring program also extends to multi-site research when the CCR is the coordinating center.

This trial will be monitored by personnel employed by a CCR contractor. Monitors are qualified by training and experience to monitor the progress of clinical trials. Personnel monitoring this study will not be affiliated in any way with the trial conduct.

# **10 STATISTICAL CONSIDERATIONS**

#### 10.1 STATISTICAL HYPOTHESES

#### 10.1.1 Primary efficacy endpoints

The primary efficacy endpoint is response to therapy as defined by a composite endpoint.

The primary objective is to evaluate the anti-tumor activity of CRLX101 at the recommended phase II dose (RP2D) combined with enzalutamide with respect to treatment response, defined as  $\geq$ 50% PSA decline or stable disease on imaging following 5 months of treatment in participants with progressive mCRPC following enzalutamide treatment.

#### 10.1.2 Secondary Efficacy endpoints

The secondary efficacy endpoints are duration of response, overall survival, and safety.

The secondary objectives are to evaluate the duration of response as defined by a sustained >30% decline in PSA, overall survival, and changes in measurable disease as determined by Response Evaluation Criteria in Solid Tumors (RECIST) and Prostate Cancer Working Group 3 (PCWG3) for the treatment combination; and to validate the recommended phase 2 dose (RP2D) of CRLX101 in combination with enzalutamide.

#### 10.2 SAMPLE SIZE DETERMINATION

For the first 3 to 6 participants, there will be a lead-in period of two cycles to ensure the safety and tolerability of CRLX101 in combination with enzalutamide. CRLX101 will be started at a dose of 12 mg/m^2, administered via IV infusion on Day 1. Based on limited potential for overlapping toxicity and well-characterized pharmacokinetics for both enzalutamide and CRLX101, it is anticipated 3 participants will participate in the lead-in phase. An accrual ceiling of 6 participants for the lead-in phase will be used to account for possible dose adjustments based on DLTs.

Following the 3- to 6-participant lead-in cohort, this study will comprise a single arm cohort of participants with mCRPC eligible for treatment following prior disease progression while on enzalutamide therapy. Based on data derived from a retrospective cohort analysis, the estimated mPFS of participants with mCRPC who failed two prior therapies (all participants received docetaxel first line, followed by either cabazitaxel, enzalutamide, or abiraterone acetate) and were receiving third line of treatment (cabazitaxel, enzalutamide or abiraterone acetate) was 4 months (n = 260 participant; IQR – 3 to 8 months). The ORR (defined as the percentage of participants with a PSA decline of  $\geq$ 50%) of this participant population was 24%. The reported data for participants receiving a 4th line of treatment (n = 38 participants) showed a mPFS of 5 months (IQR - 3 to 12 months) and an ORR of 16%. The most common therapy sequence of the third line treatment cohort was docetaxel followed by abiraterone acetate or enzalutamide then cabazitaxel (n = 110 participants), which demonstrated an ORR of 28% with a mPFS of 5 months (IQR of 3 to 9 months).(66)

The goal is to determine if the addition of CRLX101 with enzalutamide following prior enzalutamide failure could improve current response rates. Response to therapy will be assessed as a composite endpoint (biochemical response defined as 50% decline in PSA or clinical response defined as stable disease on bone scan after 5 months); attaining either of these

endpoints will be considered a success. To see at least minimal potential improvement beyond  $\sim$ 35% of participants, the goal is to rule out a 25% cohort specific response (success) rate and target a 50% success rate.

Following the three- to six-participant lead-in cohort, the trial will be conducted using an optimal two-stage phase II trial design to rule out an unacceptably low success rate of 25% ( $p_0 = 0.25$ ) in favor of an improved success rate of 50% ( $p_1 = 0.50$ ). With an alpha = 0.10 (probability of accepting a poor treatment = 0.10) and beta = 0.20 (probability of rejecting a good treatment = 0.20), this trial will enroll 8 evaluable participants. If 0 to 2 of the 8 participants have success, no further clinical evaluation will be warranted for this combination treatment. If 3 or more of the 8 evaluable participants have success, then accrual will continue until a total of 21 evaluable participants with a success, this will be considered inadequate for further investigation while if there are 8 or more participants out of 21 with a success, then this will be considered worthy of further investigation for subsequent trials. Under the null hypothesis (25% success rate), the probability of early termination is 67.9%

Participants who receive at least one dose of the study treatment will be evaluable for safety. Participants who receive at least one dose of CRLX101 and have a follow-up imaging study will be evaluable for efficacy in an overall study report but the participants in the two-stage portion of the trial will be the primary cohort for efficacy analysis. The maximum number of evaluable participants enrolled in the lead-in component will be 6 participants (anticipation to enroll 3 participants). With up to 6 participants explored in the lead-in portion, and up to 21 participants in the two-stage portion of the trial, up to 27 evaluable participants would need to be enrolled onto the trial. To allow for a small number of inevaluable participants, the accrual ceiling will be set at 30 participants.

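### The 25% null is tested on a PSA-or-stable-disease composite, but the only response benchmarks given are PSA-only, and the 0.10 false-positive rate has almost no margin above 25%

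*Combined protocol and SAP*

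**What the plan says.** Section 10.2 takes its historical response data from one retrospective cohort. The ORR there is "defined as the percentage of participants with a PSA decline of" at least 50%. It was 24% in third line ("of this participant population was 24"), 16% in fourth line (n = 38), and 28% for the commonest third-line sequence (n = 110). The section also quotes progression-free survival (PFS). The third-line median "was 4 months (n = 260 participant", IQR 3 to 8 months. The fourth-line median was 5 months, as it was for the commonest sequence, "which demonstrated an ORR of 28% with a mPFS of 5 months".

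The trial's own success criterion is wider: a 50% PSA decline, or "clinical response defined as stable disease on bone scan after 5 months", with either one counting. The study calendar (Section 3.4) places the primary assessment at C6D1. Section 10.2 then says "To see at least minimal potential improvement beyond" about 35% of participants, "the goal is to rule out a 25% cohort specific response (success) rate and target a 50% success rate". What the 35% measures is not explained, and it is not used as p0.

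The design is an optimal two-stage plan: continue with 3 or more successes in 8, and call the regimen worthy of further investigation with 8 or more in 21. One false-positive rate is given ("probability of accepting a poor treatment = 0.10") and one early-termination probability, 67.9%, labelled as applying at 25%. Section 10.4.2 reports the success proportion with 80% and 95% intervals.

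**The concern.** The benchmark data and the tested endpoint measure different things. p0 = 25% lies inside the PSA-only range of 16% to 28%, although the text does not say where it comes from. In the same population and time window, a PSA-or-stable-disease rate cannot be below its PSA component, and it rises with every participant who is stable without a PSA response. A null that suits PSA decline may therefore be too low for the composite.

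The go/no-go decision is at stake. If the composite rate on an ineffective regimen is above 25%, the rule passes such regimens more often than stated, and stage 1 stops them less often. A reader could also take 8/21 as an improvement on the 16–28% response rates printed in the same section, although some or all of the 8 successes may be stable disease only.

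**Working it through.** **Inputs (Section 10.2).** p0 = 0.25, p1 = 0.50, alpha 0.10, beta 0.20; n1 = 8, continue at 3 or more; N = 21, so n2 = 13; positive at 8 or more.

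**Formulas.** For a true success rate p:
- P(declared worthy) = Σ over x = 3 to 8 of Bin(x; 8, p) × P(Bin(13, p) ≥ 8 − x)
- P(early termination) = P(Bin(8, p) ≤ 2)

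**The plan's own figures.** At p = 0.25, early termination is 0.1001 + 0.2670 + 0.3115 = 0.6785, the stated 67.9%. The false-positive rate is 0.2076×0.2060 + 0.0865×0.4157 + 0.0231×0.6674 + 0.0038×0.8733 + a remainder of about 0.0004 = 0.0979. At p = 0.50 power is 0.8110. A full search also returns 8 then 21, with these cut-offs, as the optimal design. The arithmetic is right at 25%.

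**Same rule at other composite nulls.**

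| True composite null | P(declared worthy) | P(early termination) |
|---|---|---|
| 20% | 0.032 | 0.797 |
| 25% | 0.098 | 0.679 |
| 28% | 0.162 | 0.603 |
| 30% | 0.215 | 0.552 |
| 35% | 0.371 | 0.428 |
| 40% | 0.539 | 0.315 |
| 45% | 0.692 | 0.220 |

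The false-positive rate equals 0.10 at p = 0.251 and 0.20 at p = 0.295.

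**How much stable disease it takes.** Write the composite as the PSA rate plus the share of the cohort that is stable without a PSA response. The size of that share is an assumption.

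| PSA rate | +0 points | +5 points | +10 points |
|---|---|---|---|
| 16% | 0.01 | 0.04 | 0.12 |
| 24% | 0.08 | 0.19 | 0.34 |
| 28% | 0.16 | 0.31 | 0.47 |

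From 24%, 25.1 − 24 = 1.1 points are enough to pass 0.10. From 28%, none are needed.

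**What the documents imply about the null.** C6D1 falls after five 28-day cycles: 140 days, or about 4.6 months. That lies between the third-line PFS median (4 months) and upper quartile (8 months), so between 25% and 50% of that cohort was progression-free at the assessment. PFS is only a proxy for stable disease. Against this, participants must have progressed on enzalutamide (Section 2.1.1), and those taking it need not stop (Section 3.1). The state without CRLX101 activity is thus close to enzalutamide continued past progression, whereas the cohort was receiving a further line of cabazitaxel, enzalutamide or abiraterone. The documents do not quantify the former. The quoted PSA rates also carry no time point; if they count declines at any time, they may exceed the 5-month rate.

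**A bare pass.** 8/21 = 38.1%. Clopper–Pearson intervals, not adjusted for the two stages, are 23.6–54.4% (80%) and 18.1–61.6% (95%).

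**The case against.** The strongest reply is that every single-arm false-positive rate is conditional on p0, and the plan says as much: 25% is the rate to be ruled out, and the 67.9% is labelled as holding there. p0 may be a chosen decision floor, not an estimate of historical control. This stands: the 0.10 and 67.9% are correct at 25% and should be kept. But Section 10.2 also states the aim of improving current response rates and supports it only with PSA-only rates, so a reader will connect the two.

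Second, the direction of any error is unknown. The cohort's patients were receiving another line of treatment, while here the comparator state is close to continued enzalutamide after failure on it. The null PSA rate may be below 24%, and at a 20% composite null the false-positive rate is only 0.03. This also stands. A reader might infer that p0 is wrong, or that the real false-positive rate is 0.37 or more. The documents support neither: the higher nulls in the table are scenarios, and the PFS bounds come from a different treatment setting and endpoint.

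Third, separate reporting may seem covered, because Section 6.3 analyses PSA and measurable-lesion changes and Section 10.1.2 lists changes in measurable disease. Neither commits to the two component proportions at C6D1 with intervals.

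Finally, this is a pilot, and a pass leads only to further trials. That limits the harm, but the fix is correspondingly cheap.

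**Conclusion.** The point holds as a gap between benchmark and endpoint, combined with a rule that has almost no tolerance above its null. The computed probabilities are exact, given independent participants and the cut-offs as written. The true composite null is not established, so inflation of the false-positive rate is plausible but not demonstrated. If the null were 28% to 40%, the rate would be 0.16 to 0.54; at 20% it would be 0.03.

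The reported proportion and its intervals do not depend on p0 and can be set against any benchmark. What does not follow is that reaching 8/21 shows improvement over the 16–28% PSA rates. This should be fixed, because it changes what the trial can conclude at almost no cost.

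**What to change.** 1. In Section 10.2, keep 0.10 and 67.9%, labelled as holding at a 25% composite null, and add beside them the false-positive and early-termination probabilities for composite nulls of about 20–45% (first table above).
2. In Section 10.4.2, report the PSA-decline proportion and the stable-disease-only proportion at C6D1 separately, each with 80% and 95% intervals. Compare only the PSA component with the 16–28% benchmarks, noting that those carry no time point.
3. Keep the 8/21 rule, but state that meeting it is evidence against a 25% composite rate only, and is not by itself evidence of improvement over the quoted PSA-only rates.
4. In the same edit, state the basis of p0 for the composite, or that none is available, and say what the 35% refers to.

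The cost is some text, one table and two extra proportions, with no added participants and no change in cut-offs. The downside is a less favourable, more qualified statement of the error rate and conclusion. Raising the final cut-off is a separate trade-off for the sponsor and not part of this fix: power at a 50% success rate falls from 0.81 to 0.74 at 9/21 or more, 0.63 at 10/21 or more, and 0.48 at 11/21 or more.
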